9.2.4 Multiplicity Adjustment

Multiplicity adjustment is not applicable since only descriptive summaries are provided.

9.3 Safety Analyses

For all safety analyses, the safety analysis population will be used.

Safety variables to be summarized include vital signs, adverse events, clinical laboratory results (hematology, chemistry, and urinalysis), and quantitative parameters from 12-lead ECGs. Vital signs will be summarized in terms of observed values and changes from baseline.

9.3.1 Exposure

A subject's data for the extent of exposure to study drug will be generated from the study drug administration page of the CRF. Dosing information for individual subjects will be listed. Extent of exposure will be summarized by number of days on TD-9855 and cumulative doses of TD-9855 in Part C.

In Part C, the following will be summarized as an analysis of exposure:

- Number and percent of subjects with at least one dose of TD-9855 by dose level (
 (overall and by visits)
- Individual subject's change of dose level over time (graph)
- Descriptive summary of dose by visits
- Study drug compliance using the categories (100%; 95%; 90%; 80%; < 80%)

Study drug compliance (as percentage) can be derived as (Number of doses taken / Total expected dose) x 100, where,

- Number of doses taken = total number of doses released (number of pills x dose level) - total number of doses returned (number of pills x dose level)
- Total expected dose = dose level x number of days

Study drug administration (date/time and study day) will be provided in a data listing.

9.3.2 Adverse Events

Adverse events will be coded to the preferred terms of the Medical Dictionary for Regulatory Activities (MedDRA®). Summaries will be presented by system organ class (SOC),

preferred term (PT) and severity, and the frequency and percentage of subjects reporting each observed event.

A TEAE will be defined as any AE that begins on or after the date of first dose of study drug up to the date of last dose of study drug plus 30 days. AEs observed during the period from obtaining informed consent to the start of administration of study drug will be regarded separately from TEAEs.

All AEs and all TEAEs will be listed by subject. AEs will also be summarized by relationship to treatment (study drug) and severity.

Data listings will be provided for all subjects who experience an SAE. Data listings will also be provided for subjects who discontinued the study due to any AE, as well as for a SAE.

9.3.3 Prior and Concomitant Medications

Medications will be summarized both prior and during the treatment period. Listing will be provided for prior and concomitant medications overall.

9.3.4 Vital Signs

Vital signs will be summarized in terms of observed values (by time point), changes from baseline (by time point). When multiple values exist for the same nominal time point (e.g., duplicate reading), the average of the readings taken for vital signs will be used in the data analysis. All recorded values for vital signs data will be presented in a by-subject listing. Vital signs outliers will be flagged in the listing (Table 2).

Table 2. Vital Signs Outlier Thresholds

Heart Rate Systolic Blood Pressure		Diastolic Blood Pressure
(bpm) (mmHg)		(mmHg)
<40	<85	<45
>110	>160	>100

A sustained elevation in supine vital signs (the mean value of BP or HR) is defined as the elevation above a given threshold at three or more consecutive on-treatment measurements. For example, elevation at pre-breakfast, pre-lunch measurement on one visit as well as pre-breakfast measurement at the subsequent visit will be considered as

sustained elevation; on the other hand, elevation at pre-breakfast but not at pre-lunch for 3 consecutive visits will not constitute as "sustained" elevation.

Categorical elevated vital signs are defined in Table 3 and Table 4. Number of subjects with elevated vital signs will be summarized by visits in Part C.

Table 3. Threshold for Elevated Supine Vital Sign

Measurements	Thres	hold
Increase from Baseline in SBP	≥ 20	≥ 30
(mmHg)		
Increase from Baseline in DBP	≥ 10	≥ 20
(mmHg)		
Increase from Baseline in HR	≥ 10	≥ 20
(bpm)		
Post-baseline value SBP (mmHg)	≥ 140	≥ 160
Post-baseline value DBP (mmHg)	≥ 90	≥ 100
Post-baseline value HR (bpm)	≥ 100	≥ 120

Table 4. Combined Criteria for Elevated Supine Vital Sign

Combined Criteria
SBP ≥ 140 and Increase from Baseline ≥ 20
DBP ≥ 90 and Increase from Baseline ≥ 10
HR ≥ 100 and Increase from Baseline ≥ 20
SBP ≥ 160 and Increase from Baseline ≥ 20
DBP ≥ 100 and Increase from Baseline ≥ 10
HR ≥ 120 and Increase from Baseline ≥ 20

In addition, the following will also be summarized.

- a decrease in systolic blood pressure (a mean value of SBP) from supine to standing of ≥ 20 (and 30) mmHg and/or
- a decrease in diastolic blood pressure (a mean value of DBP) from supine to standing of ≥ 10 mmHg
- an increase in heart rate (a mean value of HR) from supine to standing of ≥ 30 bpm and/or
- an observed HR ≥ 120 bpm upon standing

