6.3.7 Orthostatic Standing Test

The orthostatic standing test (including supine blood pressures) will be performed at the time points listed in Table 1 for Part A and Table 2 for Part C and according to the details provided in the footnotes of each table.

At each time point, BP and HR measurements will be recorded with automated (or manual) sphygmomanometer while supine at 5 and 10 min (with the torso and head elevated 30 degrees from horizontal), after seated at 5 and 10 min and after 1, 3, 5, and 10 min while

standing. The standing time will be measured with a chronometer and the duration of standing will be recorded. The total duration of standing may occur in between the timepoints (ie, 1, 3, 5, and 10 minutes) for the standing test, or the subject may be able to stand for longer than the 10-minute standing test. In either case, the total duration should be recorded. More details related to the sequence of dosing and orthostatic assessments are described in [Table 1](#) for Part A and [Table 2](#) for Part C.

Blood pressure and HR collected after 10 minutes supine and seated from the orthostatic standing test will be used for safety vital sign assessment.

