6.3.8 Supine Blood Pressure

Supine blood pressure will be measured at specified time points in the Schedule of Procedures / Assessments Table 1 for Part A and [Table 2](#) for Part C.

In Part C, on Days 8, 22, 57 and 113, supine blood pressures will be collected twice in the morning before eating (after 5 and 10 minutes resting at 30° elevation), and twice again at least 4 hours after dosing (but no more than 7 hours and before lunch) after 5 and 10 minutes resting at 30° head and torso elevation (Table 2). On Day -2, supine blood pressures should be measured after 5 and 10 minutes resting at 30° head and torso elevation.

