8.3.10 Vital Signs Data

Vital signs data, including body weight, will be summarized in terms of observed values (by time point), changes from baseline (by time point).

When multiple values exist for the same nominal time point (eg, duplicate reading), the average of the readings taken for vital signs will be used in the data analysis. All recorded values for vital signs data will be presented in a by-subject listing.

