8.2 Efficacy Variables

Primary Efficacy Endpoint

For Part C, the primary endpoint is the improvement from baseline in the Likert scale "dizziness, lightheadedness, feeling faint, or feeling like you might black out" (OHSA, question 1) at week 4. A responder in Part C is defined as a subject who demonstrates at least a 2 unit decrease (improvement) from baseline in the OHSA question 1 at week 4. The raw data is in ordinal scale and will be treated as continuous variable to get the descriptive statistics.

Secondary Efficacy Endpoint

The secondary endpoints for Part C include:

- Change from baseline in the composite OHSA, OHDAS, and OHQ score
- Change from baseline in standing SBP
- Change from baseline in seated SBP
- Duration of standing during the orthostatic standing test
- Change from Supine SBP to Seated SBP

For the Supine and Seated blood pressure, the summary table will be based on the average value of the 5 minutes and 10 minutes measurements. The composite OHSA score is calculated by the non-missing average score of the 6 OHSA items. Similarly for the composite OHDAS score is the non-missing average of the 4 items. The composite OHQ score is the average of the OHSA and OHDAS composite scores.

For Change from time-matched placebo in seated SBP, calculate the area under the effect curve from 0 to 12 hours (AUC0_12) using the following trapezoidal rule. Calculation of AUC0_12 will use observed data points (actual time). If there is missing data for seated SBP, AUC will not be calculated. Here is the formula for AUC:

$$AUC_{0-t} = \frac{\sum_{i=1}^{I-1} (y_i + y_{i+1})(t_{i+1} - t_i)}{2}.$$

where

 y_i = the value of the parameter at the i-th time point,

 t_i = the i-th time point, and

I = the number of time points used in the AUC calculation.

A hypothetical example is given below to illustrate the calculation.

			Al	UC Calcula	tion	
Nominal Time Point (H)	Actual Time Point (H)	Parameter Value (Y_i)	T_diff= T_(i+1) - T_i	Y_sum= Y_(i+1) + Y_i	T_diff x Y_sum	AUC _{0_12}
0	0	1.5				
4	2.01	2.2	2.01	3.7	7.437	
7	3.91	3.4	1.9	5.6	10.64	
9	8.05	2.8	4.14	6.2	25.668	
12	23.95	2.1	11.87	4.8	56.976	50.361

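### The SAP does not say which supine reading its safety counts use, departs without comment from the protocol's 10-minute reading, and lists no table of subjects with any-time or sustained supine elevation in Part C.

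*SAP*

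**What the plan says.** **Which reading.** Protocol 6.3.7 states: "Blood pressure and HR collected after 10 minutes supine and seated from the orthostatic standing test will be used for safety vital sign assessment". That sentence covers the standing test only. Protocol 6.3.8 adds stand-alone supine measurements: "on Days 8, 22, 57 and 113, supine blood pressures will be collected twice in the morning before eating", and again after dosing, each time at 5 and 10 minutes. It does not say which of the two is the safety value. Protocol 8.3.10 has an averaging rule: "When multiple values exist for the same nominal time point (eg, duplicate reading), the average of the readings taken for vital signs will be used". SAP 9.3.4 repeats that rule.

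SAP 8.2, under efficacy variables, says that for supine and seated pressure "the summary table will be based on the average value of the 5 minutes and 10 minutes measurements". SAP 9.3.4 defines sustained supine elevation on a mean value, in a rule that begins "A sustained elevation in supine vital signs (the mean value of BP or HR", but does not identify the readings averaged.

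**How elevations are counted.** SAP Tables 3 and 4 set the criteria, for example "SBP ≥ 160 and Increase from Baseline ≥ 20". The counting rule is: "Number of subjects with elevated vital signs will be summarized by visits in Part C". A sustained elevation means "elevation above a given threshold at three or more consecutive on-treatment measurements", and the worked example in 9.3.4 crosses from one visit to the next. In SAP Appendix 2 the only count table for vital signs, 14.3.11.2, is by visit.

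**The concern.** The drug is meant to raise blood pressure. Protocol 1.4 names an increase in blood pressure as an important potential risk, and supine hypertension can lead to dose reduction and discontinuation in Part C. There is no data monitoring committee, and SAP section 1 says the results will guide further development. A reader of the report will want to know how many treated subjects had raised supine pressure at any time, and how many had it persistently.

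The plan leaves two gaps. The reading behind the count is unclear, so two programmers could produce different numbers from the same data. And the planned table cannot give an on-drug incidence, because by-visit percentages cannot be added up. The by-visit series is also affected by dropout. SAP 6.4 removes subjects without a measurement from that time point's denominator, and SAP section 3 has dosing discontinued when supine hypertension persists after a dose reduction. Subjects who stop for the risk being measured leave the later percentages.

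**Working it through.** The documents give no figure on this point to reproduce. The supine pressure distribution, the drift between readings and the within-subject correlation are all assumed below. The thresholds and the schedule come from the documents.

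**1. On-drug days with supine pressure (protocol Table 2).** Standing-test days: 1, 2, 15, 29, 85, 140 (6 days). Stand-alone days: 8, 22, 57, 113 (4 days). Total 10. The 10-minute rule in protocol 6.3.7 therefore covers 6 of the 10.

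**2. Two readings, one threshold (160 mm Hg).**
- 156 then 163: mean (156 + 163)/2 = 159.5. Elevated on the 10-minute reading, not on the mean.
- 166 then 158: mean (166 + 158)/2 = 162. Elevated on the mean, not on the 10-minute reading.

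**3. Share at or above 160 in a population.** Assume a 10-minute SBP with mean 150, between-subject SD 18 and reading SD 7.
- 10-minute reading: SD = √(18² + 7²) = √373 = 19.31; P = 1 − Φ(10/19.31) = 30.2%.
- Mean of two readings: SD = √(18² + 7²/2) = √348.5 = 18.67, and mean = 150 − d/2, where d is the rise from 5 to 10 minutes; P = 1 − Φ((10 + d/2)/18.67).

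| d (mm Hg) | Share on 5/10-minute mean | Share on 10-minute reading |
|---|---|---|
| +8 | 22.7% | 30.2% |
| +4 | 26.0% | 30.2% |
| 0 | 29.6% | 30.2% |
| −4 | 33.4% | 30.2% |
| −8 | 37.4% | 30.2% |

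The sign of the difference follows the sign of d, which the documents do not give. With no drift the two definitions differ by 0.6 percentage points.

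**4. From by-visit rate to any-time count.** Assume 15% elevated on each of the 10 days, with an equicorrelated normal variable behind each elevation.
- Same subjects every time: 15%.
- Correlation implied by the SDs in step 3: 18²/(18² + 7²) = 324/373 = 0.87. Any-time share about 31%.
- Correlation 0.5: about 52%.
- Independent days: 1 − 0.85¹⁰ = 80.3%. This is a mathematical limit and is not consistent with the SDs in step 3.

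The same by-visit table is compatible with any of these values.

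**5. The sustained count is a different quantity.** There are 18 on-treatment time points: one after dosing on Day 1, one on the morning of Day 2, and two on each of the other 8 days. Simulating 10% elevated at each point gives 37.5% ever elevated and 9.8% sustained at correlation 0.7, and 49.8% and 8.2% at correlation 0.5. Neither number can stand in for the other, and Appendix 2 lists a table for neither.

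**The case against.** Five points can be made for the plan.

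- **A reader might infer that averaging undercounts elevations.** The documents do not support that. They do not say whether supine pressure rises or falls between 5 and 10 minutes, and step 3 shows an overcount if it falls.
- **A reader might infer that elevations are assessed only visit by visit.** That is wrong: the sustained rule spans visits. What stands is that no listed table reports it. By its own example, it also leaves out elevations seen only before breakfast at three consecutive visits.
- **A reader might take the 10-minute reading as the protocol's rule for every supine safety value.** It is stated for the standing test only. The 5/10-minute mean in turn sits under efficacy variables, so carrying it into SAP 9.3.4 is a reasonable inference but is not written there. If 5 and 10 minutes count as one nominal time point, protocol 8.3.10 would itself allow averaging. That supports calling this an ambiguity, but protocol 6.3.7 lists the two as separate measurements and picks one for safety.
- **Elevations are not hidden.** The SAP plans a by-subject listing with outliers flagged, individual supine plots and heatmaps, and a subject count of 24-hour SBP outliers. Clinically significant abnormalities that meet the definition are recorded as adverse events and tabulated per subject. This stands, and it limits the point to the summary tables.
- **The averaging choice does not drive dosing.** Dose reduction rests on the Investigator's determination with Sponsor agreement. This also stands.

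**Conclusion.** Two gaps hold. First, protocol 6.3.7, SAP 8.2 and SAP 9.3.4 do not agree on the supine value for safety, and the SAP declares no departure. The effect on counts is of unknown direction. Under the assumed distribution it is 0.6 percentage points with no drift and about 7 points either way with a drift of 8 mm Hg. Second, no listed table gives subjects with any-time or sustained supine elevation, and by-visit percentages cannot supply either. This is the more important gap: 15% per day is compatible with 15% of subjects ever elevated, or about 31% at a correlation near 0.87. The 80% for independent days should not be read as a plausible value, because readings within a subject will be correlated. All these percentages are illustrations. The two gaps themselves rest on the text alone. The point is worth correcting because the risk is a named one and the data are already collected, but it does not mean that elevations would go unseen.

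**What to change.** In SAP 9.3.4 and Appendix 2:

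1. For each Table 3 and Table 4 criterion, add the number (%) of treated subjects meeting it at any on-treatment reading from the first Part C dose to the last dose, and the number (%) with a sustained elevation. Use all treated subjects as the denominator. State that unscheduled and out-of-window readings count towards the any-time row, since SAP 6.1 and 6.3 otherwise leave them out of summaries.
2. Use the 10-minute reading for these counts on standing-test days, as protocol 6.3.7 states. Name the reading used on the stand-alone days (8, 22, 57, 113), where the protocol gives no rule.
3. Reconcile protocol 6.3.7, SAP 8.2 and SAP 9.3.4 in one sentence that says which readings enter the mean and where the mean applies.
4. Show the counts on the 5/10-minute mean as a sensitivity summary.

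The cost is SAP wording and a few extra table rows, with no new data. The drawbacks are that a single reading is slightly noisier than the mean of two (SD 19.3 against 18.7 in the assumed model), and that the report will carry two supine definitions, which must be labelled.

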9.3.5 ECG

The QTcF, PR interval, QT interval, QRS duration, and HR from standard digital ECGs will be summarized by study visit in terms of observed values, changes from baseline, and counts and percentages within appropriately defined categories Table 5.

≥ 480 ≥ 500

Heart Rate QTcF PR Heart Change from PR Percentage QRS change from Baseline **Change From** Interval **QTcF** Baseline Rate Interval Baseline (%) (msec) (bpm) (bpm) (msec) (msec) (msec) >120 ≥20 ≥ 200 ≥ 15 ≥ 120 Males: ≥30 >130 ≥ 220 ≥ 25 >30. ≤ 60 > 60 Optional: ≥ 430 ≥ 240 ≥ 450 ≥ 260 ≥ 470 ≥ 280 ≥ 480 ≥ 300 ≥ 500 Females: ≥ 450 ≥ 470

Table 5. Vital Sign and ECG Outlier Thresholds

Treatment emergent ECG abnormalities are defined as those not present at baseline, or those that worsened after treatment, e.g., borderline at baseline, but were prolonged after treatment.

When multiple values exist for the same nominal time point (eg, triplicate reading), the average of the readings taken for ECG parameters will be used in the data analysis, including the outlier analysis stated above in table 4.

All recorded values for the ECG parameters will be presented in a by-subject listing. A listing of subjects with outliers will also be provided.

9.3.6 Clinical Laboratory Results

The study used a mixture of local and central labs, lab units, normal ranges will be converted using the Standard International lab unit if possible. Lab data will be counted as Low, Normal, and High for each visit by applying the local lab normal ranges. Lab shift tables from baseline to discharge/follow-up will be summarized.

Clinical laboratory test results will be listed by subject. Reference ranges provided by the laboratory for each parameter will be used to evaluate the clinical significance of laboratory test results. Values falling outside of the relevant reference range will be flagged, as appropriate, in the data listings. Abnormalities in clinical laboratory test results will be listed in a separate listing.

Cumulative urine volume over the 24-hour period for each dosing day will be summarized by Study Day and dose.

9.4 Interim Analyses

This interim analysis will be performed after all enrolled subjects have completed 4 weeks of study in Part C. The interim will include the analyses for primary, secondary, additional efficacy endpoints, and safety endpoints. The final analysis (includes all visits) will be performed after all subjects have completed Part C.

Appendix 1: Reporting Structures for Data Summary

Reporting Structures

C: Continuous endpoints will be presented with an 8-point summary using the following reporting structure, unless otherwise noted,

```
N x
Mean (SD) x.xx (x.xx)
Median x
Q1, Q3 xx.x, xx.x
Minimum, Maximum xx.x, xx.x
```

F: Frequency endpoints will be presented by a 3-point summary using the following reporting structure, unless otherwise noted,

```
n X
Count (%) X (xx.x)
```

MF Categorical variables (multiple frequency) will be presented by a 3-point summary using the following reporting structure, unless otherwise noted, where the sum of the category n's is the total n

```
n X Category 1 count (%) x (x.x) Category 2 count (%) x (x.x)
```

NLSM: Normal distribution (continuous) endpoint least-square mean (LS mean) summaries will be presented using the following structure, unless otherwise noted:

```
Evaluable n xx

LS Mean (SE) xxx.x (xx.xx)

LS Mean Difference (SE) xxx.x (xx.xx)

95% CI for LS Mean Difference (xxx.x, xxx.x)

P-value vs. {Placebo} 0.xxx
```

BLSM: Binomial distribution (binary/proportion) endpoint generalized least-square mean (LS mean) summaries will be presented using the following structure, unless otherwise noted:

PLSM: Poisson distribution (count) endpoint generalized least-square mean (LS mean) summaries will be presented using the following structure, unless otherwise noted:

```
Evaluable n xx LS Mean Count (SE) xxx.x (xx.xx)
```

```
LS Mean Difference (SE) xxx.x (xx.xx) 95% CI for LS Mean Difference (xxx.x, xxx.x) P-value vs. {Placebo} 0.xxx
```

NBLSM: Negative binomial distribution (rate/ratio) endpoint generalized least-square mean (LS mean) summaries will be presented using the following structure, unless otherwise noted:

```
Evaluable n xx

LS Mean Annual Rate x.xx

Ratio (TD-XXXX / {placebo}) x.xx

95% CI for Ratio (x.xx, x.xx)

Percent Reduction vs. {Placebo} 0.xx

95% CI for Percent Reduction (0.xx, 0.xx)

P-value vs. {Placebo} 0.xxx
```

KM: Time to event summaries will be summarized with the following reporting structure:

For the primary endpoint and secondary endpoints under multiplicity control, an additional p-value line will be included in the reporting summary:

```
Adjusted P-value vs. Placebo 0.xxx
```

Appendix 2: List of TFLs (Part C only)

Table Number	Table Name
14.1	Subject Disposition, Demographic and Baseline Characteristics
14.1.1	Subject disposition
14.1.2	Demographics and Baseline Characteristics
14.1.2.2	Baseline Characteristics (additional)
14.1.3	Medical History
14.1.4	Summary of Exposure
14.1.4.1	Prior medications by ATC class and preferred term
14.1.4.2	Concomitant medications by ATC class and preferred term
14.2	Efficacy
14.2.1	Summary of Change in the Likert Scale Post Study Drug Administration by Visit
14.2.1.1	Summary of Change in the Likert Scale Post Study Drug Administration by Visit and Dose
14.2.1.2	Summary of Change in the Likert Scale Post Study Drug Administration by Subgroups (over time and at Day 29 only)
14.2.2	Summary of Change in Composite OHSA Score Post Study Drug Administration by Visit
14.2.2.1	Summary of Change in Composite OHSA Score Post Study Drug Administration by Visit and Dose
14.2.2.2	Summary of Change in Composite OHSA Score Post Study Drug Administration by Subgroups
14.2.3.1	Summary of Change in Physician Global Assessment Post Study Drug Administration
14.2.3.2	Summary of Change in Subject Global Assessment Post Study Drug Administration

Summary of Physician Global Assessment Post Study Drug Administration
Summary of Subject Global Assessment Post Study Drug Administration
Summary of Change in OH Daily Activity Scale Post Study Drug Administration
Summary of Change in Composite OHDAS Score Post Study Drug Administration by Visit
Summary of Change in Composite OHDAS Score Post Study Drug Administration by Visit and Dose
Summary of Change in Composite OHDAS Score Post Study Drug Administration by Subgroups
Summary of Change in Composite OHQ Score Post Study Drug Administration by Visit
Summary of Change in Composite OHQ Score Post Study Drug Administration by Visit and Dose
Summary of Change in Composite OHQ Score Post Study Drug Administration by Subgroups
Summary of Subject Satisfaction Survey Post Study Drug Administration
Summary of proportion of responders on OHSA #1 by Visit
Summary of proportion of responders on OHSA #1 by Visit and Dose
Summary of proportion of responders on OHSA #1 by Visit (and at Day 29) and Dose and Subgroups
Summary of Change in Standing Duration Post Study Drug Administration by Visit
Summary of Change in Standing Duration Post Study Drug Administration by Visit and Dose
Summary of Change in Standing Duration Post Study Drug Administration by Subgroups

14.2.7.3	Summary of Actual Value in Standing Duration Post Study Drug Administration
14.2.7.4	Shift from Baseline to Day 29 on Actual Value - Standing Duration
14.2.8.1	Summary of Change in Seated SBP Post Study Drug Administration by Visit
14.2.8.1.1	Summary of Change in Seated SBP Post Study Drug Administration by Visit and Dose
14.2.8.1.2	Summary of Change in Seated SBP Post Study Drug Administration by Subgroups
14.2.8.2	Summary of Change in Seated DBP Post Study Drug Administration
14.2.9.1	Summary of Change in Supine SBP Post Study Drug Administration by Visit
14.2.9.1.1	Summary of Change in Supine SBP Post Study Drug Administration by Visit and Dose
14.2.9.1.2	Summary of Change in Supine SBP Post Study Drug Administration by Subgroups
14.2.9.2	Summary of Change in Supine DBP Post Study Drug Administration
14.2.10.1 – 14.2.10.4	Summary of Change in 1 min Standing SBP Post Study Drug Administration (and 3 min, 5 min, 10 min) by Visit
14.2.10.1.1 – 14.2.10.4.1	Summary of Change in 1 min Standing SBP Post Study Drug Administration (and 3 min, 5 min, 10 min) by Visit and Dose
14.2.10.1.2 – 14.2.10.4.2	Summary of Change in 1 min Standing SBP Post Study Drug Administration by Subgroups (and 3 min, 5 min, 10 min)
14.2.11.1 – 14.2.11.4	Summary of Change from Seated SBP to 1 min Standing SBP Post Study Drug Administration (and 3 min, 5 min, 10 min)
14.2.12.1 – 14.2.12.4	Summary of Change from Supine SBP to 1 min Standing SBP Post Study Drug Administration (and 3 min, 5 min, 10 min)
14.2.15.1	Summary of Change from Supine SBP to Seated SBP Post Study Drug Administration by Visit
14.2.15.1.1	Summary of Change from Supine SBP to Seated SBP Post Study Drug Administration by Visit and Dose

Figure 15.2.1.1	Individual Change from Baseline in Vital Signs - Seated SBP over Time
Figure 15.2.1.2	Mean+/-SD Change from Baseline in Vital Signs - Seated SBP over Time
Figure 15.2.1.2.1	Mean+/-SD Change from Baseline in Vital Signs - Seated SBP over Time by Subgroups
Figure 15.2.1.3	Individual Actual Value in Vital Signs - Seated SBP over Time
Figure 15.2.1.4	Mean +/ SD Actual Value in Vital Signs - Seated SBP over Time
Figure 15.2.2.1	Individual Change from Baseline in Vital Signs - Seated DBP over Time
Figure 15.2.2.2	Mean+/-SD Change from Baseline in Vital Signs - Seated DBP over Time
Figure 15.2.3.1.1	Individual Change from Baseline in Vital Signs - 1 min Standing SBP over Time
Figure 15.2.3.1.2	Mean+/-SD Change from Baseline in Vital Signs - 1 min Standing SBP over Time
Figure 15.2.3.1.2.1	Mean+/-SD Change from Baseline in Vital Signs - 1 min Standing SBP over Time by Subgroups
Figure 15.2.3.1.3	Individual Actual Value in Vital Signs - 1 min Standing SBP over Time
Figure 15.2.3.1.4	Mean +/ SD Actual Value in Vital Signs - 1 min Standing SBP over Time
Figure 15.2.3.2.1	Individual Change from Baseline in Vital Signs - 3 min Standing SBP over Time
Figure 15.2.3.2.2	Mean+/-SD Change from Baseline in Vital Signs - 3 min Standing SBP over Time

Figure 15.2.3.2.2.1	Mean+/-SD Change from Baseline in Vital Signs - 3 min Standing SBP over Time by Subgroups
Figure 15.2.3.2.3	Individual Actual Value in Vital Signs - 3 min Standing SBP over Time
Figure 15.2.3.2.4	Mean +/ SD Actual Value in Vital Signs – 3 min Standing SBP over Time
Figure 15.2.3.3.1	Individual Change from Baseline in Vital Signs - 5 min Standing SBP over Time
Figure 15.2.3.3.2	Mean+/-SD Change from Baseline in Vital Signs - 5 min Standing SBP over Time
Figure 15.2.3.3.2.1	Mean+/-SD Change from Baseline in Vital Signs - 5 min Standing SBP over Time by Subgroups
Figure 15.2.3.3.3	Individual Actual Value in Vital Signs - 5 min Standing SBP over Time
Figure 15.2.3.3.4	Mean +/ SD Actual Value in Vital Signs – 5 min Standing SBP over Time
Figure 15.2.3.4.1	Individual Change from Baseline in Vital Signs - 10 min Standing SBP over Time
Figure 15.2.3.4.2	Mean+/-SD Change from Baseline in Vital Signs - 10 min Standing SBP over Time
Figure 15.2.3.4.2.1	Mean+/-SD Change from Baseline in Vital Signs - 10 min Standing SBP over Time by Subgroups
Figure 15.2.3.4.3	Individual Actual Value in Vital Signs - 10 min Standing SBP over Time
Figure 15.2.3.4.4	Mean +/ SD Actual Value in Vital Signs – 10 min Standing SBP over Time
Figure 15.2.4.1.1	Individual Change from Baseline in Vital Signs - Change from Seated SBP to 1 min Standing SBP over Time
Figure 15.2.4.1.2	Mean+/-SD Change from Baseline in Vital Signs - Change from Seated SBP to 1 min Standing SBP over Time

Figure 15.2.4.2.1	Individual Change from Baseline in Vital Signs - Change from Seated SBP to 3 min Standing SBP over Time
Figure 15.2.4.2.2	Mean+/-SD Change from Baseline in Vital Signs - Change from Seated SBP to 3 min Standing SBP over Time
Figure 15.2.4.3.1	Individual Change from Baseline in Vital Signs - Change from Seated SBP to 5 min Standing SBP over Time
Figure 15.2.4.3.2	Mean+/-SD Change from Baseline in Vital Signs - Change from Seated SBP to 5 min Standing SBP over Time
Figure 15.2.4.4.1	Individual Change from Baseline in Vital Signs - Change from Seated SBP to 10 min Standing SBP over Time
Figure 15.2.4.4.2	Mean+/-SD Change from Baseline in Vital Signs - Change from Seated SBP to 10 min Standing SBP over Time
Figure 15.2.5.1.1	Individual Change from Baseline in Vital Signs - Change from Supine SBP to 1 min Standing SBP over Time
Figure 15.2.5.1.2	Mean+/-SD Change from Baseline in Vital Signs - Change from Supine SBP to 1 min Standing SBP over Time
Figure 15.2.5.2.1	Individual Change from Baseline in Vital Signs - Change from Supine SBP to 3 min Standing SBP over Time
Figure 15.2.5.2.2	Mean+/-SD Change from Baseline in Vital Signs - Change from Supine SBP to 3 min Standing SBP over Time
Figure 15.2.5.3.1	Individual Change from Baseline in Vital Signs - Change from Supine SBP to 5 min Standing SBP over Time
Figure 15.2.5.3.2	Mean+/-SD Change from Baseline in Vital Signs - Change from Supine SBP to 5 min Standing SBP over Time
Figure 15.2.5.4.1	Individual Change from Baseline in Vital Signs - Change from Supine SBP to 10 min Standing SBP over Time
Figure 15.2.5.4.2	Mean+/-SD Change from Baseline in Vital Signs - Change from Supine SBP to 10 min Standing SBP over Time
Figure 15.2.6.1	Individual Change from Baseline in Vital Signs - Supine SBP over Time
Figure 15.2.6.2	Mean+/-SD Change from Baseline in Vital Signs - Supine SBP over Time

Figure 15.2.6.2.1	Mean+/-SD Change from Baseline in Vital Signs - Supine SBP over Time by Subgroups
Figure 15.2.6.3	Individual Actual Value in Vital Signs - Supine SBP over Time
Figure 15.2.6.4	Actual Value in Vital Signs - Supine SBP over Time
Figure 15.2.7.1	Individual Change from Baseline in Vital Signs - Supine DBP over Time
Figure 15.2.7.2	Mean+/-SD Change from Baseline in Vital Signs - Supine DBP over Time
Figure 15.2.8.1	Individual Change from Baseline in Vital Signs - Standing Duration over Time
Figure 15.2.8.2	Mean+/-SD Change from Baseline in Vital Signs - Standing Duration over Time
Figure 15.2.8.2.1	Mean+/-SD Change from Baseline in Vital Signs - Standing Duration over Time by Subgroups
Figure 15.2.8.3	Individual Percent Change from Baseline in Vital Signs - Standing Duration over Time
Figure 15.2.8.4	Individual Percent Change from Baseline in Vital Signs - Standing Duration over Time – All Subjects
Figure 15.2.8.5	Mean+/-SD Percent Change from Baseline in Vital Signs - Standing Duration over Time
Figure 15.2.8.6	Individual Actual Value in Vital Signs - Standing Duration over Time
Figure 15.2.8.7	Individual Actual Value in Vital Signs - Standing Duration over Time – All Subjects and Part C Completers
Figure 15.2.8.8	Mean+/-SD Actual Value in Vital Signs - Standing Duration over Time
Figure 15.2.9.1	Individual Vital Signs - Seated and Standing SBP Heatmap
Figure 15.2.10.1	Individual Vital Signs - Seated and Standing DBP Heatmap

Figure 15.2.11.1	Individual Vital Signs - Supine SBP Heatmap
Figure 15.2.12.1	Individual Vital Signs - Supine DBP Heatmap
Figure 15.2.13.1	Bar Plot of Change from Baseline in Vital Signs - Seated SBP by Dose and Change Subgroup
Figure 15.2.14.1	Bar Plot of Change from Baseline in Vital Signs - Standing Duration by Dose and Change Subgroup
Figure 15.2.14.2	Bar Plot of Percent Change from Baseline in Vital Signs - Standing Duration by Dose and Percent Change Subgroup
Figure 15.2.15.1	Bar Plot of OHSA Question 1 Change from Baseline Pre-Lunch
Figure 15.2.15.2	Bar Plot of OHSA Question 1 Change from Baseline Pre-Lunch for Baseline Value > 2
Figure 15.2.15.3	OHSA Question 1 - Actual Value for Individual Subject over Time
Figure 15.2.15.4	OHSA Question 1 - Actual Value for Individual Subject over Time - All Subjects and Part C Completers
Figure 15.2.15.5	Mean +/ SD Change from Baseline in OHSA Question 1 over Time
Figure 15.2.15.6	OHSA Composite Score - Actual Value for Individual Subject over Time
Figure 15.2.15.7	OHSA Composite Score - Actual Value for Individual Subject over Time - All Subjects and Part C Completers
Figure 15.2.15.8	Mean +/ SD Change from Baseline in OHSA Composite Score over Time
Figure 15.2.15.9	OHDAS Composite Score - Actual Value for Individual Subject over Time
Figure 15.2.15.10	OHDAS Composite Score - Actual Value for Individual Subject over Time - All Subjects an Part C Completers
Figure 15.2.15.11	Mean +/ SD Change from Baseline in OHDAS Composite Score over Time

Figure 15.2.15.12	OHQ Composite Score - Actual Value for Individual Subject over Time
Figure 15.2.15.13	OHQ Composite Score - Actual Value for Individual Subject over Time - All Subjects and Part C Completers
Figure 15.2.15.14	Mean +/ SD Change from Baseline in OHQ Composite Score over Time
Figure 15.2.16.1	Individual Plots in 24 Hours Vital Signs Monitor - Systolic Blood Pressure over Time
Figure 15.2.16.2	Individual Plots in 24 Hours Vital Signs Monitor - Diastolic Blood Pressure over Time
Figure 15.2.16.3	Individual Plots in 24 Hours Vital Signs Monitor - Heart Rate over Time
Figure 15.2.16.4	Individual Plots in 24 Hours Vital Signs Monitor - Mean Arterial Pressure over Time
Figure 15.2.17.1	Individual Change from Baseline in Vital Signs - Change from Supine SBP to Seated SBP over Time
Figure 15.2.17.2	Mean +/ SD Change from Baseline in Vital Signs - Change from Supine SBP to Seated SBP over Time
Figure 15.2.17.3	Mean +/ SD Change from Baseline in Vital Signs - Change from Supine SBP to Seated SBP over Time by Subgroups
Figure 15.2.17.4	Individual Actual Value in Vital Signs - Change from Supine SBP to Seated SBP over Time for All Subjects and Part C Completers
Figure 15.2.17.5	Mean +/ SD Actual Value in Vital Signs - Change from Supine SBP to Seated SBP over Time
14.3	Safety
14.3.1	Extent of Exposure
14.3.1.1	Study Drug compliance
14.3.1.2	Summary of Exposure by Visit
14.3.1.3	Number (%) of Subjects with Exposure by Visit
13.3.2	Overview of adverse events
14.3.3.1	Treatment-emergent adverse events by system organ class and preferred term

14.3.3.2	Treatment-emergent adverse events by preferred term
14.3.4	Treatment-emergent adverse events occurring in >2% subjects by preferred term and sorted by decreasing frequency
14.3.5	Treatment-emergent adverse events by system organ Class, preferred term, and maximum severity
14.3.6	Treatment-emergent adverse events by system organ Class, preferred term, and Treatment Relationship
14.3.7	Study drug related treatment emergent adverse events by system organ class and preferred term
14.3.8.1	Serious adverse events by preferred term
14.3.8.2	Serious adverse events by system organ class and preferred term
14.3.10.1	Shift Table of Laboratory values from baseline to Worst Increase by laboratory test group, lab parameters
14.3.10.2	Shift Table of Laboratory values from baseline to Worst Decrease by laboratory test group, lab parameters
14.3.11.1	Summary of vital signs and Change from baseline by parameter and visit
14.3.11.2	Number (%) of patients with potentially clinically significant Changes in vital signs by visit
14.3.12.1	Summary of ECG and Change from Baseline by parameters and visit
14.3.12.2	Number (%) of patients with abnormal ECG and Changes by categories by parameters and visit
Figure 14.3.1	Individual Change of Exposure over Time - All Subjects

Listings

Number	Title
16.2.1	Subject disposition
16.2.2	Demographic and baseline characteristics
16.2.4	Prior and concomitant medications
16.2.5	OHSA score
16.2.6	OHDAS score
16.2.7	Clinical global impression (Global Assessment Score from Physician and Subject)
16.2.8	Extent of exposure (including duration between Part A and Part C)
16.2.9.1	Adverse events
16.2.9.2	Serious adverse events
14.2.9.3	Adverse events leading to drug discontinuation
14.2.9.4	Treatment Emergent Adverse Events with Concomitant Medications
16.2.10	Vital signs (Seated BP, Standing BP, Supine BP, Standing Duration)
16.2.10.2	24 Hours Vital Signs Monitor
16.2.11	ECGs
16.2.12	Clinical laboratory results (hematology, chemistry, urinalysis)
16.2.13	Study Drug Accountability
16.2.14	Major Protocol Deviation
